This study aims to address the existing gap in knowledge by conducting a comprehensive comparison of the incidence of hypocalcemia in patients undergoing thyroidectomy using Ligasure versus conventional ligation of vessels by knot tying. Additionally, secondary outcomes such as operative time, intraoperative bleeding, length of hospital stay, and postoperative complications will be assessed to provide a holistic understanding of the two surgical approaches.

Hypothesis:

The incidence of hypocalcemia in patients undergoing thyroidectomy using Ligasure is less versus conventional ligation of vessels by knot tying.

Operational definition:

1)Hypocalcemia: Patients having calcium level below 8.0 mg/dL will be labelled as hypocalcemia.

Material and methods:

1)Study design:

Randomized control trial

2)Study setting:

Surgical unit I Gulab Devi hospital, Lahore

3) Duration of study:

6 months after approval of study.

4)Sample size:

Sample size will be 76 patients (38 in each group) calculated by WHO calculator, with confidence interval of 95% and margin of error 5%, power of test at 90% taking 6.7 % in Liga Sure⁷ vs 32.4% in conventional knot tying technique⁸.

5)Sampling technique:

Non-probability purposive sampling for including patients in study and random allocation for grouping of patients using lottery method.

6)Sample Selection:

Inclusion criteria:

1) Patients from both genders.

2) Age between 20 years to 50 years.

3) Patients undergoing Total thyroidectomy for benign thyroid disease.

Exclusion criteria:

1) Patients having pre-operative hypocalcaemia.

2) Patients having malignant thyroid disease.

3)Patients having recurrent thyroid disease.

4)Patients having lobectomy + isthmectomy.

5)Patients having pro-operative calcium supplements.

Data collection procedure:

After approval from hospital ethical committee, 76 patients (38 in each case) will be enrolled presenting in department of Surgery, Gulab Devi Hospital, Lahore for total thyroidectomy. Informed consent will be taken from each patient. Demographic information including age and address will be noted. Patients will be divided into two groups by using lottery method.

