Group A will be managed with Ligasure and group B will be managed with conventional ligation of vessels by knot tying. All the patients will be subjected to their treatment according to their respective groups by single experienced surgeon having minimum experience of five years. Calcium levels will be taken pre operatively, 24 and 48 hours postoperatively. All the data will be collected in a pre-designed proforma. All information regarding patients will be kept confidential and bias will be addressed by single blind data collection procedure.

Data Analysis:

Statistical analysis will be done using Statistical Package for Social Sciences (SPSS) version 24. Mean and standard deviation was calculated for all quantitative variables like age, BMI, serum calcium level. Qualitative data like gender, presence of hypocalcemia will be presented as frequencies and percentages. Chi square test will be applied to compare two treatments effectiveness by taking P value 0.05 as significant.

References:

4. Mishra V. Comparative study between harmonic scalpel and ligasure vessel sealing system: in open and laparoscopic surgery. World J Laparosc Surg. 2013;6(2):74-6.

7. Ahmed H. Khafagy a, Ibrahim Abdelnaby. Total thyroidectomy: Ligasure versus Clamp & Knot technique for intraoperative hemostasis. Egyptian Journal of Ear, Nose, Throat and Allied Sciences (2013) 14, 59–65.

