## STATISTICAL ANALYSIS PLAN

## A Comparative Analysis of Hypocalcemia Incidence in Patients Undergoing Thyroidectomy: Ligasure vs Conventional Ligation of vessels by knot tying.

**NCT Number:** NCT06716632

**Objectives:** To compare the incidence of postoperative hypocalcemia between LigaSure and conventional knot-tying techniques in total thyroidectomy patients.

**Methods**: A randomized controlled trial was conducted at the Surgical Department of Gulab Devi Hospital, Lahore, from July 2024 to January 2025. Seventy-six patients who underwent total thyroidectomy for benign thyroid disease were randomly allocated to the LigaSure (n=38) and conventional knot-tying (n=38) groups. Serum calcium levels were measured preoperatively and at 24/48 hours postoperatively. For statistical analysis, SPSS v24 was used and non-parametric tests like the Mann-Whitney U and chi-square tests were used.

**Results:** Differences found in operative time (p=0.106), intraoperative bleeding (p=0.867), hospital stay (p=0.967), or hypocalcemia incidence (LigaSure: 10.5% vs. Conventional: 7.9%; p=0.692) were of no significance.

**Conclusion:** Both techniques demonstrated comparable safety profiles with no statistically significant differences in postoperative outcomes. LigaSure offers a comparable alternative to conventional methods when used by experienced surgeons.

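### The SAP calls the techniques comparable on the strength of non-significant superiority tests, but 4/38 vs 3/38 leaves a risk ratio anywhere from 0.35 to 5.10

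*SAP*

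**What the plan says.** The protocol's Hypothesis is directional: "The incidence of hypocalcemia in patients undergoing thyroidectomy using Ligasure is less versus conventional ligation of vessels by knot tying". The Sample size section fixes 38 patients per group, with "power of test at 90% taking 6.7 % in Liga Sure⁷ vs 32.4% in conventional knot tying technique⁸". The Data Analysis section plans a chi-square test with 0.05 as the significance threshold and does not say whether it is one- or two-sided.

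The SAP is written as a results abstract. For hypocalcaemia it reports "hypocalcemia incidence (LigaSure: 10.5% vs. Conventional: 7.9%; p=0.692) were of no significance". The other outcomes are also given by p-value only: "Differences found in operative time (p=0.106), intraoperative bleeding (p=0.867), hospital stay (p=0.967". The Conclusion contains the sentence "Both techniques demonstrated comparable safety profiles with no statistically significant differences in postoperative outcomes", followed by "LigaSure offers a comparable alternative to conventional methods when used by experienced surgeons".

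Neither the protocol nor the available SAP text gives an equivalence or non-inferiority margin, or a confidence interval for a treatment effect. The 5% margin of error and 95% confidence level in the Sample size section are inputs to a sample-size calculator and serve neither purpose.

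**The concern.** A test of no difference that fails to reject supports the statement that no significant difference was found. It does not support a claim that the techniques are comparable. That claim needs a margin chosen in advance and an interval lying inside it, or at least an interval narrow enough to exclude differences that matter. The SAP has neither and makes the claim twice.

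The point estimate also runs against the hypothesis: LigaSure has the higher observed rate. A reader of the Conclusion could take the techniques as interchangeable for hypocalcaemia when seven events in total cannot show that. The Conclusion does not mention that the conventional-arm rate fell far below the planning assumption, so the reader is not told why the test was so uninformative.

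**Working it through.** **Inputs.** SAP: 38 per arm, 10.5% vs 7.9%, p=0.692. Protocol, Sample size: planned rates 6.7% and 32.4%. Protocol, Data Analysis: threshold 0.05.

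**1. Counts and the reported p-value.** The SAP prints percentages only. Of 38, only 4 rounds to 10.5% and only 3 rounds to 7.9%. Pearson chi-square without continuity correction:

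76 × (4×35 − 3×34)² / (38 × 38 × 7 × 69) = 0.157, p=0.6916.

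This reproduces 0.692, a two-sided value. Expected events are 7/2 = 3.5 per arm; Fisher's exact p is 1.00.

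**2. Risk difference.** 4/38 − 3/38 = 0.0263. Wilson 95% limits are 4.2% to 24.1% (LigaSure) and 2.7% to 20.8% (conventional). Newcombe:

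- lower: 0.0263 − √[(0.1053−0.0417)² + (0.2080−0.0789)²] = −0.118
- upper: 0.0263 + √[(0.2413−0.1053)² + (0.0789−0.0272)²] = +0.172

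Other methods agree: score −11.5 to +17.4 points, Wald −10.4 to +15.6, Agresti-Caffo −11.3 to +16.3.

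**3. Risk ratio.** (4/38)/(3/38) = 1.33. The score 95% CI is 0.35 to 5.10. The log interval can be checked by hand: SE = √(1/4 − 1/38 + 1/3 − 1/38) = 0.7285, and 1.333 × exp(±1.96 × 0.7285) gives 0.32 to 5.56. The adjusted log interval is 0.34 to 4.83.

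**4. What would have passed as comparable.** Chi-square p-values for other LigaSure counts against 3/38 conventional:

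| LigaSure | p |
|---|---|
| 0/38 | 0.077 |
| 1/38 | 0.304 |
| 6/38 | 0.287 |
| 8/38 | 0.103 |
| 9/38 (23.7%) | 0.059 |
| 10/38 | 0.033 |

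Both complete elimination of hypocalcaemia and a tripled rate would have been non-significant.

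**5. Planning assumption against outcome.** Expected conventional events: 38 × 0.324 = 12.3; observed 3. The ratio of rates is 7.9/32.4 = 0.24, and P(3 or fewer events at 32.4%) = 0.0004. The planned reduction, 32.4 − 6.7 = 25.7 points, exceeds even the Wilson upper limit of 20.8% for the conventional rate. The planned risk ratio, 0.067/0.324 = 0.207, lies below the 95% lower limit by all three methods. At 99% the score interval (0.249 to 7.24) still excludes it, but the log interval (0.204 to 8.71) does not.

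**6. Power at the rates seen.** Exact binomial enumeration, 38 per arm, rejecting when the two-sided chi-square p is 0.05 or less. The true conventional rate is an assumption: 7.9% as observed, with the Wilson limits as the range.

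| True conventional rate | Power at risk ratio 0.207 | Chance of missing a doubled LigaSure rate | Chance of missing a tripled rate |
|---|---|---|---|
| 2.7% | 2% | 94% | 83% |
| 7.9% | 22% | 80% | 51% |
| 20.8% | 64% | 49% | 3% |

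At 7.9%, even a true LigaSure rate of zero would reach significance only 35% of the time.

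**7. For scale only.** The documents give no margin, so these are assumed. With 7.9% in both arms, one-sided 0.025 and 80% power, non-inferiority needs (1.960 + 0.842)² × 2 × 0.079 × 0.921 / margin² patients per arm: about 457, 115 or 51 for margins of 5, 10 or 15 points. The trial had 38.

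**The case against.** The case for leaving the text alone is that the Conclusion states its own basis (no significant differences), limits itself to experienced surgeons, and sits beside the rates, p-values and group sizes, so a careful reader can work out the imprecision. It is a reporting matter that changes no design or test. All of that is true, but none of it supports the word *comparable*, and the Conclusion is the sentence most readers will use.

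A second objection concerns sidedness. The hypothesis is directional, and 38 per group fits a one-sided calculation (37 to 39 per group) better than a two-sided one (45 to 56). Under a one-sided 0.05 rule and a 7.9% conventional rate, power rises from 22% to 38% for the planned risk ratio and from 35% to 59% for a zero LigaSure rate. A result of 0/38 vs 3/38 would then be significant (0.077/2 = 0.039). This dependence should be acknowledged. The two-sided figures match the p-value the SAP reports, and power is low either way.

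Third, power computed at the observed rate adds little to the confidence interval. That is fair: the finding rests on steps 2 and 3, and steps 4 to 6 only illustrate it.

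Fourth, part of the SAP was not available for review, so a margin or interval may be stated there. That cannot be ruled out, but it would not narrow the interval these counts give.

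**Conclusion.** The concern holds. The SAP's results support a statement that no significant difference was found. They do not support either claim of comparability. The 95% limits run from 11.8 points fewer to 17.2 points more hypocalcaemia with LigaSure, and from about a third of the conventional risk to about five times it. The upper absolute limit is more than twice the observed conventional rate (17.2/7.9 = 2.2).

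The data do say something: at the 95% level they argue against the relative benefit the trial was sized for, and the planned absolute reduction was not plausible at the conventional rates these data support. Smaller benefits and sizeable harms remain open.

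This rests on inferred counts of 4 and 3, which the reported p-value confirms. The choice of interval method does not alter the reading. The power figures also assume a true conventional rate and a two-sided test; the verdict does not need them.

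**What to change.** Keep the planned chi-square test. Report the risk difference and risk ratio with 95% CIs beside it, naming the methods, and give Fisher's exact p (1.00) as a sensitivity result because two expected counts are 3.5. Replace both sentences of the Conclusion with wording such as:

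> LigaSure was not shown to reduce postoperative hypocalcaemia (10.5% vs 7.9%; difference +2.6 points, 95% CI -11.8 to +17.2; risk ratio 1.33, 95% CI 0.35 to 5.10). The conventional-arm rate was far below the 32.4% assumed in the sample size. The risk-ratio interval excludes the planned relative reduction (risk ratio 0.21), but smaller benefits and sizeable harms remain possible. The trial was not designed to show equivalence and does not show it.

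Two related details should be completed, although the verdict does not depend on them.

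- **Event definition.** The protocol says "Patients having calcium level below 8.0 mg/dL will be labelled as hypocalcemia" and "Calcium levels will be taken pre operatively, 24 and 48 hours postoperatively", but not whether the 24-hour value, the 48-hour value or either one defines an event. State which was used.
- **Scope of the safety claim.** Postoperative complications are a secondary outcome in the Objective, yet the available SAP text reports none apart from hypocalcaemia. Report them by arm if they were recorded; otherwise confine the conclusion to the outcomes shown.

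**Cost.** The wording, both intervals and the sensitivity p-value come from figures already printed. The two details need the trial records. The downside is a less favourable conclusion.
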